from Schultheis et al. (10) was designed to explore whether addition of regorafenib to FOLFOX or FOLFIRI could be feasible as a treatment of mCRC, in terms of safety and pharmacokinetic interactions of the various drug components of the regimen. Forty-five patients were treated every 2 weeks with 5-fluorouracil 400 mg/m^2 bolus then 2400 mg/m^2 over 46 h, folinic acid 400 mg/m^2, and either oxaliplatin 85 mg/m^2 or irinotecan 180 mg/m^2. On days 4–10, patients received regorafenib 160 mg orally once daily. Drug-related adverse events resulted in dose modification, dose interruption, or permanent discontinuation of study treatment in 31 (69%) patients overall (18 [72%] FOLFOX and 13 [65%] FOLFIRI). Dose reduction or dose interruption of at least one of the chemotherapy components was observed in 52% of patients treated with FOLFOX and 65% of patients receiving FOLFIRI. A dose reduction of 5-fluorouracil due to AEs was necessary in 18% of administered cycles. 5-Fluorouracil administration was omitted in 8% of cycles. Oxaliplatin and irinotecan doses were reduced in 11% and 12% and interrupted in 11% and 5% of administered cycles, respectively. Actually, regorafenib had acceptable tolerability in combination with chemotherapy. The most frequent grade 3-4 AEs were: neutropenia (45%), Hand-Foot Skin Reaction (15%), diarrhea (10%), and hypophosphatemia (12%). Regarding pharmacokinetics, area under the curve (AUC) of irinotecan was significantly higher in cycle 2 (following regorafenib dosing) than in cycle 1 (before regorafenib dosing); the ratio of AUC values (cycle 2:cycle 1) was 1.28 (90% confidence interval [CI] 1.06 –1.54). Cmax of irinotecan was only slightly increased, and t1/2 was unchanged. For SN-38, AUC was significantly higher in cycle 2 than in cycle 1 (ratio 1.44, 90% CI 1.12–1.85), while Cmax was unchanged. In line with the known elimination pathways of platinum and 5-fluorouracil, no pharmacokinetic interaction with regorafenib was seen (10). The study from O'Neil et al. (11) was designed to show whether the addition of regorafenib to FOLFIRI improves PFS (over a placebo-FOLFIRI arm) when given as second-line therapy for patients treated initially with oxaliplatin and fluoropyrimidine-based therapy. The regorafenib/FOLFIRI schedule that was used was the one proposed by Schultheis et al. (10) (i.e. standard FOLFIRI with irinotecan 180 mg/m^2 plus regorafenib 160 mg daily from day 4 to 10). The study met its primary endpoint of demonstrating that the addition of regorafenib to FOLFIRI prolongs PFS compared to FOLFIRI alone with a HR of 0.72. When looking at tumor response, authors found that regorafenib (combined to chemo) provided more partial responses than placebo plus chemo (35% vs. 19%, p= 0.045). The combination was very tolerable, with little increase in toxicity compared to the control chemotherapy regimen. Of note, regarding the top-3 reported severe (gr. 3-4) AEs, neutropenia, diarrhea, and hypophosphatemia were reported in 41%, 15%,

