#### Non-Hematologic DLT:

- Missing > 7 days daily doses of regorafenib due to drug-related toxicity (scheduled treatment pause of regorafenib will not be counted),
- Grade  $\geq 3$  (NCI-CTCAE V5) non-hematologic toxicity, except:
  - Grade 3 nausea, vomiting, diarrhea and grade 2 alopecia
  - any untreated HFSR that can be adequately controlled with medical intervention,
  - Grade  $\geq 3$  lipase elevation without signs of pancreatitis,

- Grade ≥ 2 posterior reversible encephalopathy syndrome (PRES),
- Grade ≥ 2 retinopathy,
- Liver-specific DLTs are:
  - Drug-related gr. 3-4 bilirubin increase
  - Drug-related gr. 3-4 AST and/or ALT increase
  - Drug-related AST and/or ALT increase > 3 x ULN and associated with concurrent bilirubin increase(> 2 x ULN)

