## Phase I

DLT monitoring must be performed during the first three cycles of treatment. Patients will be treated until disease progression.

In case of patient withdrawal before completing the entire third cycle for reasons other than DLT, a new patient will be included at this dose level.

The phase I part of this study will be designed as a standard 3+3 design for dose escalation/de-escalation and 3 to 6 patients will be enrolled in each cohort sequentially, depending on occurrence of dose limiting toxicities (Figure 1).

A standard 3 + 3 design will be followed in the dose escalation part of study.

Three dose levels for Irinotecan/Regorafenib (IRI 150/REGO 120, IRI 180/REGO 120, IRI 180/REGO 160) are planned as well as a -1 level (IRI 150/REGO 80) to be opened in case of maximum tolerated dose (MTD) was reached at level 1 (Table 1).

Table 1 :

Steps	Dose Levels	Number of patients
DL-1	IRI 150/REGO 80	0-6
DL1	IRI 150/REGO 120	3-6
DL2	IRI 180/REGO 120	3-6
DL3	IRI 180/REGO 160	3-6

At each dose level, three patients will be included. Three additional patients will be enrolled at the same dose level if one dose limiting toxicity (DLT) is observed in the first three patients of this dose level (Figure 1).

Figure 1 :

[figure not shown]

Table 2 : Dose escalation rules

Outcome (# DLT / # Patients)	Action
0 DLT out of the first 3 patients	Include 3 patients at the next dose level
1 DLT out of 3 patients	Include 3 additional patients at the same dose level.
$\geq 2$ DLT out of 3 patients	Stop dose escalation. Include 3 additional patients at the previous dose level (unless 6 subjects were already treated).
$\geq 2$ DLT out of 6 patients	Stop dose escalation. Include 3 additional patients at the previous dose level (unless 6 patients were already treated).

The MTD is defined as the dose at which at least two out of three to six patients experienced a DLT during the first three cycles of treatment.

Dose escalation will be stopped if MTD is reached or the last dose level (IRI 180/REGO 160) is reached (MTD not reached).

The recommended phase II dose (RP2D) is defined as the dose closest to the MTD at which a DLT is observed in 0/3 or 1/6 patients.

Should any patient discontinue the study prior to completing the entire (3 cycles) for reasons other than a DLT then a replacement patient will be added at that dose level.

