Including skin assessment for toxicities

Pre-menopausal women of childbearing potential only

12-lead ECG will be performed before and after the administration of Oxaliplatin during the three first cycles (Phase I and II) beyond cycle 3, ECG will be performed before administration of oxaliplatin

Includes: albumin, creatinine, creatinine clearance calculated according MDRD, lipase, glucose, TSH (every 6 weeks of CXD1), , total protein and uric acid

Liver function tests will be performed weekly during the three first cycles of treatment

Not required at day 1 of cycle 1 if those were completed within 7 days

Dipstick assessment with pH, protein, glucose, bilirubin, ketones, blood cells and leucocytes

CT scan of the abdomen, pelvis and chest or if the patient is allergic to iodine contrast agents, hepatic MRI and CT scan of the pelvis and chest without injection; RECIST criteria version 1.1

CT-Scans will be performed every 8 weeks

If the last radiological tumor assessment > 1 month

CT-Scan of safety follow-up will be performed if only it weren't done at the EOT visit

Period for DLT assessment is the three first cycles (only Phase I)

Height only at screening

Blood pressure will be monitored every other week during the first 3 cycles of treatment

Continuously from screening until FU visit, 30 days after last administration of study drug

A treatment diary will be handed over to patient on cycle 1 day 1

Three EDTA tubes will be collected at baseline, every 8 weeks during treatment and at the end of treatment

Paraffin-embedded human solid tissue blocks will be sent off at room temperature at the end of the enrollments

Only for unstabilized adverse events since the end of treatment

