### 5.3 Treatment period

After all screening assessments have been completed and the patient's eligibility has been confirmed and documented, the patient will be enrolled.

**The following assessments should be performed on the first day of each cycle (FOLFIRINOX + Regorafenib except C1D1 prior to receiving study treatment (+/- 3 days) :**

- DLTs assessment for phase I from C2D1 to C4D1 (three first cycles),
- Physical examination with weight, body surface area (if the patient's body weight changes by more than 10 % then BSA will be recalculated for Regorafenib and it will be recalculated for any change of weight for Irinotecan). The physical examination includes skin assessment for toxicities,
- ECOG performance status,
- Adverse events documentation (including Start/Stop dates, seriousness, CTC notation and grading, relationship to study drug, outcome and action taken) using CTCAE V5.0,
- Concomitant medications (including start/stop dates, dose, indication),

- 12-lead ECG : It will be performed before and after oxaliplatin administration during the three first cycles of Phase I/II,
- The following laboratory evaluations are not required at Day 1 of Cycle 1 if these were completed within 7 days of starting study drug treatment. Otherwise, these laboratory evaluations are required on Day 1 of each cycle:
  - ➔ CBC with differential should be performed: RBC, hemoglobin, hematocrit, platelet count and WBC. WBC must include differential neutrophil, lymphocyte, monocyte, basophil and eosinophil counts,
  - ➔ Coagulation panel: Prothrombin time (PT) or the International Ratio of PT (PT-INR) and Partial Thromboplastin Time (PTT)  
If a patient is on warfarin or phenprocoumarone with stable PT/INR at baseline, the PT/INR should be assessed on Day 15 of Cycle 2. If either of these values is above the acceptable range, the doses should be modified and the assessments should be repeated every fortnight until it is stable,
  - ➔ Electrolyte panel: sodium, potassium, chloride, magnesium, calcium, bicarbonates, phosphate,
  - ➔ Chemistry panel : albumin, lipase, glucose, serum creatinine, clearance calculated according MDRD, uric acid, , protein total, TSH every 6 weeks,
  - ➔ Hepatic panel: Aspartate Amino-Transferase (AST), Alanine Amino-Transferase (ALT), bilirubin (total and direct), GGT, alkaline phosphatase, Lactic Dehydrogenase (LDH).
- Urine analysis: PH, protein, glucose, bilirubin, ketones, blood cells and leukocytes
- Drug dispensing,

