**With this treatment, prophylactic G-CSF will be systematically given after each course from Day 7 to Day 12.**

### **REGORAFENIB administration (Phase I and II):**

-On days 4–10 of each cycle, all patients will receive Regorafenib orally once daily depending on dose levels for phase I and RPD2 for phase 2.

- 1 cycle = 15 days

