**Table 11 : Dose modifications and measures for HFSR**

Skin toxicity grade	Occurrence	Recommended dose modification and measures
Grade 1	Any	Maintain dose level and immediately institute supportive measures for symptomatic relief.
Grade 2	1st occurrence	Decrease dose by 40 mg (one tablet) and institute supportive measures. If no improvement occurs despite dose reduction, interrupt therapy for a minimum of 7 days, until toxicity resolves to Grade 0-1. A dose re-escalation is permitted at the discretion of the investigator.
	No improvement within 7 days or 2nd occurrence	Interrupt therapy until toxicity resolves to Grade 0-1. When re-starting treatment, decrease dose by 40 mg (one tablet). A dose re-escalation is permitted at the discretion of the investigator.
	3rd occurrence	Interrupt therapy until toxicity resolves to Grade 0-1. When re-starting treatment, decrease dose by 40 mg (one tablet). A dose re-escalation is permitted at the discretion of the investigator.
	4th occurrence	Discontinue treatment with regorafenib permanently.
Grade 3	1st occurrence	Institute supportive measures immediately. Interrupt therapy for a minimum of 7 days until toxicity resolves to Grade 0-1. When re-starting treatment, decrease dose by 40 mg (one tablet). A dose re-escalation is permitted at the discretion of the investigator.
	2nd occurrence	Institute supportive measures immediately. Interrupt therapy for a minimum of 7 days until toxicity resolves to Grade 0-1. When re-starting treatment, decrease dose by 40 mg (one tablet).
	3rd occurrence	Discontinue treatment with regorafenib permanently.

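### The missed-dose DLT criterion cannot be met by a regorafenib hold or stop whose first missed dose falls in cycle 3, if no cycle is delayed

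*Combined protocol and SAP*

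**What the plan says.** Section 2.2.1 lists among the DLTs "Missing > 7 days daily doses of regorafenib due to drug-related toxicity (scheduled treatment pause of regorafenib will not be counted"). The synopsis gives the same threshold. Section 6.1 sets the dosing: "On days 4–10 of each cycle, all patients will receive Regorafenib orally once daily". The window is stated in section 5.1, footnote 14 ("Period for DLT assessment is the three first cycles (only Phase I")), and in section 5.3 ("DLTs assessment for phase I from C2D1 to C4D1 (three first cycles")). Under section 3.1, recruitment halts once a cohort is full and resumes by default when its patients have finished three cycles. No text says that doses missed in cycle 4 count.

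In section 2.2.1 the missed-dose line stands under the non-hematologic heading. In the synopsis it is a separate item ahead of both groups. Its wording covers any drug-related toxicity, and it is read that way here.

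The grade 3-or-higher non-hematologic line has exceptions, including "Grade 3 nausea, vomiting, diarrhea and grade 2 alopecia" and HFSR that can be adequately controlled.

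In section 3.1, Table 2 and the definitions of the MTD and RP2D rest on DLT counts alone.

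**The concern.** The sponsor chose a three-cycle window, but this criterion can be triggered only by holds that begin in the first two cycles. Two patients with the same toxicity and the same length of hold are classified differently if one misses a first dose on C2D10 and the other on C3D4. Nothing in the documents explains the difference.

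Cycle 3 is not a minor part of the window. Irinotecan is given on day 1 and regorafenib from day 4, so the first irinotecan dose precedes any regorafenib. The background section reports higher exposure after regorafenib dosing (AUC ratios of 1.28 for irinotecan and 1.44 for SN-38). Only cycles 2 and 3 test that interaction.

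Single events decide the outcome. One DLT separates 0/3 from 1/3, and 1/6 (compatible with the RP2D) from 2/6 (the MTD). A level could clear at 0/3 although every patient had stopped regorafenib in cycle 3 for a toxicity that no other line counts.

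**Working it through.** **Inputs.** Threshold: more than 7 missed doses, so at least 8 (2.2.1). Doses: days 4 to 10, so 7 per cycle (6.1). Cycle: 14 days (6.1). Last DLT assessment: C4D1 (5.3).

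**Dose calendar.** The window holds 3 × 7 = 21 doses. C4D1 is day 43 and the next dose, C4D4, is day 46, so no cycle 4 dose can be missed before assessment ends. The regorafenib paragraph of 6.1 gives a 15-day cycle. That moves C4D1 to day 46 and C4D4 to day 49, and the result is the same.

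**Reachability.** For a continuous hold of m doses with first missed dose number j, the doses missed inside the window are min(m, 22 − j). A DLT needs this to exceed 7.

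| First missed dose | Number j | Most that can be missed | Can exceed 7? |
|---|---|---|---|
| C1D4 | 1 | 21 | yes |
| C2D10 | 14 | 8 | yes |
| C3D4 | 15 | 7 | no |
| C3D10 | 21 | 1 | no |

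For m = 8, 10, 14 or a permanent stop, 14 of the 21 possible starting doses can count and 7 (33%) cannot. A hold that does count spans 15 calendar days: 8 dosing days and 7 scheduled days off.

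**Which toxicities depend on this line.**
- Grade 2 HFSR is below the grade 3 line. Table 11 says to "interrupt therapy for a minimum of 7 days, until toxicity resolves to Grade 0-1" if dose reduction does not help. Seven days alone is too short in any cycle, so only longer holds matter.
- Grade 3 nausea, vomiting and diarrhea are exempt by grade. Table 8 interrupts regorafenib for grade 3 non-hematologic events in general, with a footnote excluding non-refractory nausea and vomiting.
- Grade 3 neutropenia without fever, and platelets of 25 to 50 × 10⁹/L without bleeding, have no hematologic DLT line. Table 9 interrupts regorafenib for both.

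**Effect on clearing a level (assumptions, not data).** Let b be the DLT risk from all other lines and h the chance of a toxicity with no other DLT line that causes a hold of 8 or more doses or a permanent stop. Take b and h as independent, with first missed doses spread evenly over the 21.

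- As counted now: p = 1 − (1 − b)(1 − 2h/3)
- All such holds counted: p = 1 − (1 − b)(1 − h)
- P(clear) = (1 − p)³ + 3p(1 − p)⁵

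Example with b = 20% and h = 5%: p is 0.2267 as counted and 0.2400 with all counted, which gives 65.1% and 62.2%.

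| h (b = 20%) | P(clear), as counted | P(clear), all counted | Gap, points |
|---|---|---|---|
| 2% | 68.5% | 67.4% | 1.2 |
| 5% | 65.1% | 62.2% | 2.9 |
| 10% | 59.3% | 53.6% | 5.7 |
| 15% | 53.6% | 45.4% | 8.2 |

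For h = 5 to 15%, the gap is 3 to 10 points at b = 10% and 2 to 6 points at b = 30%.

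**The case against.** Several counter-arguments have force.

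- **Other lines catch most serious toxicity.** This stands. Grade 4 diarrhea, liver events, febrile neutropenia, bleeding and most grade 3 non-hematologic events count in cycle 3. Grade 3 HFSR that needs a hold of two weeks is hard to call adequately controlled, so the grade line plausibly catches it. Grade 3 diarrhea matters only if it stays above grade 2 for about that long or regorafenib is stopped.
- **Cycle delay.** Table 4 lets a cycle slip as far as day 29. The text does not say whether regorafenib days on the original calendar then count as missed. The result above is therefore stated for undelayed cycles.
- **Judgement.** Adverse events are part of the phase I primary endpoint. The project team may stop or modify escalation (3.1), and the Independent Safety Committee meets at the end of phase I (11.2.7). This limits the harm, but it does not correct the DLT rate or an RP2D defined by DLT counts.
- **Any duration rule in a fixed window cuts off late events.** True, but here the cut-off removes one whole cycle of three, and a short wording change avoids it.

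A reader might also infer that these patients leave the denominator, because after "patient withdrawal before completing the entire third cycle for reasons other than DLT, a new patient will be included at this dose level". The documents do not support that. Section 9.1 says that stopping treatment is not withdrawal from the trial and that such patients stay in it, so stopping regorafenib alone does not trigger replacement.

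Nor do the background rates measure the problem. The cited studies report grade 3-4 neutropenia in 41 to 45%, diarrhea in 10 to 15% and HFSR in 15%. Those figures are for any such event with two-drug chemotherapy and are not rates of 8-dose holds starting within six weeks.

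**Conclusion.** The gap is real and follows from the stated dosing days, threshold and assessment window. If no cycle is delayed, 7 of the 21 possible starting doses, all in cycle 3, cannot lead to a DLT by this criterion, even if regorafenib is stopped for good. The loss is limited to toxicities that no other line counts.

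The consequence for escalation cannot be sized from the documents. The gaps shown depend on the assumed hold rate, the other DLT risk, independence and even onset. They run from about 1 point at a 2% hold rate to 8 points at 15%, with 20% other risk. It would go too far to conclude that cycle 3 toxicity in general escapes the DLT count, or that the RP2D will be too high.

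The wording should be changed because the DLT count drives escalation, the MTD and the RP2D, and the remedy is small. Nothing here bears on the phase II sample size or error rates.

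**What to change.** In section 2.2.1 and the synopsis, replace the line with:

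> Missing > 7 scheduled daily doses of regorafenib because of a drug-related toxicity that starts in cycles 1-3. Permanent discontinuation of regorafenib for such a toxicity counts as a DLT at once. If doses are being withheld at C4D1 for such a toxicity, later scheduled doses are counted until regorafenib restarts or the 8th dose is missed.

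Align the assessment period in 5.3 and the recruitment-halt rule in 3.1, so that a running hold is resolved before the cohort decision. The threshold and the grade-based lines stay as they are. The diary and drug accountability records already capture the doses.

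The cost is time, and it falls on the whole cohort because recruitment is halted:
- First missed dose C3D4: 8th missed dose C4D4 (day 46), 46 − 43 = 3 days after C4D1.
- First missed dose C3D10: 8th missed dose C4D10 (day 52), 52 − 43 = 9 days.
- Toxicity starting after C3D10: first missed dose C4D4, 8th missed dose C5D4 (day 60), 60 − 43 = 17 days.

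A delayed cycle lengthens these waits. A permanent stop needs no wait.

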STUDY ENDPOINTS	
2. Non-Hematologic DLT:
 
 
➤ Grade <math>\geq 3</math> (CTCAE v5) non-hematologic toxicity, except:           
 
-Grade 3 nausea, vomiting, diarrhea, and Grade 2 alopecia
 
-any untreated HFSR that can be adequately controlled with medical intervention,
 
-Grade <math>\geq 3</math> lipase elevation without signs of pancreatitis,
 
 
 
➤ Grade <math>\geq 2</math> posterior reversible encephalopathy syndrome (PRES),
 
➤ Grade <math>\geq 2</math> retinopathy,
 
➤ Liver-specific DLTs are:           
 
-Drug-related gr. 3-4 bilirubin increase
 
-Drug-related gr. 3-4 AST and/or ALT increase
 
-Drug-related AST and/or ALT increase <math>> 3 \times</math> ULN and associated with concurrent bilirubin increase(<math>> 2 \times</math> ULN)
 
 
 
 
3. Hematologic DLT:
 
 
➤ Grade 4 (NCI-CTCAE v5) neutropenia lasting <math>> 3</math> days,
 
➤ Grade 3 Febrile neutropenia (ANC <math>< 1,000/\text{mm}^3</math> with fever <math>\geq 38.5^\circ\text{C}</math>) (NCI-CTCAE v5),
 
➤ Grade 4 Febrile neutropenia (life-threatening consequences; urgent intervention indicated),
 
➤ Grade 4 (NCI-CTCAE v5) anemia (i.e. life threatening consequences; urgent intervention indicated),
 
➤ Platelets <math>< 25,000/\text{mm}^3</math> or platelets <math>< 50,000/\text{mm}^3</math> associated with bleeding,
 
➤ INR or PTT elevation of Grade <math>\geq 3</math> (NCI-CTCAE v5) with associated bleeding,
 
➤ Grade <math>\geq 3</math> hemorrhage/bleeding events (NCI-CTCAE v5).
 
 
Phase II: 48-week disease-control rate (defined as the rate of non-progressing patients after central review, at 48-week post-initiation of therapy, to all treated patients).
 
Secondary endpoints:
 
Phase II :
 
Progression-free survival (PFS), defined as the time from date of inclusion to date of first observed disease progression (investigator's radiological or clinical assessment) or death due to any cause, if death occurs before progression is documented. A central review of CT-scans is planned for patients found progression-free at 48 weeks. Patients without tumor progression or death at the time of analysis will be censored at their last date of tumor assessment,

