**Prophylactic G-CSF will be systematically given after each course from Day-7 to Day 12.**

**REGORAFENIB** will be given orally at a dose of 80 to 160 mg, as per dose-level, once daily on days 4 to 10 of each cycle

Tumor assessments (computed tomography (CT) or magnetic resonance imaging (MRI)) of the chest, abdomen, pelvis (if patient allergic to iodine contrast agents) will be performed at the baseline, every 8 weeks thereafter.

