### **DLT recording and assessment**

- Study sites will document any DLT immediately and report a DLT event to the Sponsor within 24 hours of site's awareness.
- Once recruitment of 3 or 6 patients per dose level has been completed, recruitment will be halted by default until the 3-cycle dose-finding treatment has been completed for each patient and sites have reported all relevant safety findings.
- The decision to stop, modify or continue escalation will be made by the project team (coordinator, statistician, project manager, safety vigilance head and vigilance manager) if there are no SUSARs. In the event of SUSARs, we will refer the matter to the independent scientific committee.
- The Sponsor will communicate further dosage information (dose escalation or de-escalation) and additional safety measures to all participating sites/investigators.

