#### 11.2.7. INDEPENDENT SAFETY COMMITTEE (ISC)

An Independent Safety Committee (appendix 12) is organized as an Independent Data Monitoring Committee, comprising independent experts in clinical research and/or the study indication.

The ISC will be constituted of 3 persons: two oncologists and a methodologist not participating in the trial.

The first scheduled time point will be at the end of phase I. According to the number of DLTs and after the advice of the IDMC, the sponsor will decide to continue on to phase II or stop the trial. The sponsor could ask to organise an additional independent safety committee in the event of SUSARs during Phase I.

During a trial the ISC could be requested to review:

- Real-time and cumulative safety data for evidence of study-related adverse events;
- Adherence to the protocol;
- Factors that might affect the study outcome or compromise the trial data (such as protocol violations, losses to follow-up, etc.);

- Data relevant to proceeding to the next stage of the study, if applicable.

The safety data will be provided to the ISC members by the Biostatistics Unit, and / or the Clinical Research Pharmacovigilance Unit and / or the Study Coordinator.

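### Refractory grade 3 nausea, vomiting or diarrhea does not count as a DLT, so a patient with uncontrolled diarrhea in cycles 1 to 3 can be scored DLT-free

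*Combined protocol and SAP*

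**What the plan says.** Section 2.2.1 (Non-Hematologic DLT) makes drug-related grade 3 or higher non-hematologic toxicity in the first three cycles a DLT, then lists exceptions. The first is "Grade 3 nausea, vomiting, diarrhea and grade 2 alopecia". The synopsis (Study Endpoints) has the same exception: "Grade 3 nausea, vomiting, diarrhea, and Grade 2 alopecia". Neither adds a duration or a failure-of-treatment condition. The next exception does carry one: "any untreated HFSR that can be adequately controlled with medical intervention".

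A separate criterion makes it a DLT to miss more than 7 "days daily doses of regorafenib due to drug-related toxicity", not counting the scheduled pause. Regorafenib is taken "once daily on days 4 to 10 of each cycle" (synopsis, Treatment Modalities), and a cycle is 14 days.

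In section 3.1, Table 2 escalates, expands or stops on the number of DLTs. The recommended phase II dose (RP2D) is "the dose closest to the MTD at which a DLT is observed in 0/3 or 1/6 patients". Section 11.2.7 says of the choice between going on and ending the study: "According to the number of DLTs and after the advice of the IDMC, the sponsor will decide to continue on to phase II".

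The protocol recognizes refractory events only in its dosing rules (section 6.6). Table 5 has a row for diarrhea lasting over 48 hours despite high-dose loperamide, and footnote a to Table 8 separates refractory from non-refractory nausea and vomiting. Neither feeds the DLT definition.

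**The concern.** Exempting grade 3 gastrointestinal events that respond to treatment is reasonable, since otherwise manageable chemotherapy toxicity would block escalation. Exempting those that do not respond removes from the count a toxicity that bears directly on whether a dose can be given.

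That toxicity is tied to the drugs being escalated. The dose levels raise irinotecan from 150 to 180 mg/m² and regorafenib from 120 to 160 mg. Section 1 reports that exposure (AUC) after regorafenib dosing rose 1.28-fold for irinotecan and 1.44-fold for SN-38. It also reports severe diarrhea in 15% of patients against 5% on placebo when regorafenib 160 mg was added to FOLFIRI, and grade 3-4 diarrhea in 10% in the phase Ib study with doublets. This trial uses a triplet.

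A level could be passed, or named RP2D, without such events counting. The replacement rule in section 3.1 can widen the gap: a patient who leaves before completing cycle 3 because of refractory grade 3 diarrhea, with no DLT criterion met, is replaced and not counted. Phase II then treats 69 − 6 = 63 further patients at the chosen dose.

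**Working it through.** The plan states no figure that depends on this wording, so there is none to reproduce. Two things can be checked.

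**1. Does the missed-dose criterion catch these patients?** In three undelayed 14-day cycles the regorafenib days are 4-10, 18-24 and 32-38, which is 21 doses. A DLT needs at least 8 missed.

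- Any 14 consecutive days contain at most 7 dosing days, so a continuous hold of up to 14 days misses at most 7.
- The shortest continuous hold that misses 8 is 15 days, for example day 4 to day 18 (7 + 1 doses).
- Losing one whole cycle of regorafenib gives exactly 7 missed doses, which is not a DLT.
- An episode that starts in cycle 3 can miss at most 7 doses within the window, so it cannot meet the criterion by itself.
- Diarrhea confined to days 1-3 or 11-14 of a cycle costs no doses.

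**2. How much would counting the events change the 3+3 rule?** Let q be the share of patients with uncontrolled grade 3 nausea, vomiting or diarrhea in the first three cycles (assumed 2.5% to 5%). Let r be the share with any other DLT (assumed 10% or 20%).

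How often such events would be seen:

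- At least one case, 1 − (1 − q)^n: 0.073 to 0.143 for n = 3, and 0.141 to 0.265 for n = 6.
- Two or more cases: 0.0018 to 0.0073 for n = 3, and 0.0088 to 0.0328 for n = 6.

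With independent events, p = 1 − (1 − r)(1 − q). The chance that a level passes is (1 − p)³ + 3p(1 − p)² × (1 − p)³. The chance of expanding from 3 to 6 patients is 3p(1 − p)².

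| r | q | p | Pass | Expand to 6 |
|---|---|---|---|---|
| 10% | 0 (current wording) | 10% | 0.906 | 0.243 |
| 10% | 2.5% | 12.25% | 0.867 | 0.283 |
| 10% | 5% | 14.5% | 0.824 | 0.318 |
| 20% | 0 (current wording) | 20% | 0.709 | 0.384 |
| 20% | 2.5% | 22% | 0.665 | 0.402 |
| 20% | 5% | 24% | 0.622 | 0.416 |

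The fall in the pass probability is 3.9 to 8.2 points at r = 10% and 4.4 to 8.7 points at r = 20%.

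Overlap reduces this. If the added DLT probability is halved because those patients have another DLT anyway, the pass probabilities are 0.887 and 0.867 (r = 10%) and 0.687 and 0.665 (r = 20%), a fall of about 2 to 4 points. With complete overlap the fall is 0.

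As an upper-range check, add 10 or 15 points to r = 20% with no overlap. The pass probability then falls from 0.709 to 0.494 (p = 30%) or 0.396 (p = 35%).

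**The case against.** The strongest reply is that this is a deliberate choice, written the same way in both places, and that the main scenarios show no intolerable dose being passed. Total DLT probabilities of 12.25% to 24% lie below the 2/6 (33%) that stops a level, and the two with 10% other DLTs lie below the 1/6 (17%) accepted for the RP2D. On those figures the change mostly produces extra expansion and stopping. That stands for the assumed 2.5% to 5%. A level above 33% appears only in the upper-range check, with 15 points added to 20%. Fifteen percent is the rate the cited FOLFIRI trial reported for all severe diarrhea, so this is an extreme case.

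Other criteria also catch some of these patients. Grade 4 events still count, as do febrile neutropenia and other drug-related grade 3 consequences such as dehydration. Repeated regorafenib holds can add up past 7 doses; the 15-day figure covers one hold without cycle delay. This narrows the gap but does not close it.

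There is discretion as well. Graded adverse events are part of the phase I endpoint and are tabulated by dose level (section 10.3). Section 3.1 says "The decision to stop, modify or continue escalation will be made by the project team" when there are no SUSARs, and the independent committee advises at the end of phase I. In phase II, Table 5 cuts irinotecan to 120 mg/m² after a first grade 3-4 diarrhea episode. These are real safeguards, but they are descriptive, discretionary or applied patient by patient. None changes the count that the stated rule uses.

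Dosing and DLT rules may legitimately differ, so the irinotecan cut in Table 5 is not itself evidence of a defect.

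**Conclusion.** The concern holds. As written, a patient with grade 3 nausea, vomiting or diarrhea that resists treatment is DLT-free unless the event reaches grade 4, another DLT criterion is met, or more than 7 regorafenib doses are missed. The last is hard to reach in a single episode.

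The likely effect on escalation is modest: about 4 to 9 percentage points on the chance of passing a level under independence, 2 to 4 with half overlap, and none with full overlap. This rests on assumed rates for both uncontrolled events and other DLTs, because the documents give neither. The finding about the wording does not depend on those rates. The change is worth making because the toxicity is foreseeable with both escalated drugs and the correction is small.

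**What to change.** In section 2.2.1 and the synopsis, replace the exception with: *Grade 3 nausea, vomiting or diarrhea brought under adequate control by medical treatment, and grade 2 alopecia.* Add: *Grade 3 diarrhea that persists despite optimal antidiarrheal treatment (for example, more than 48 h on high-dose loperamide), and refractory grade 3 nausea or vomiting, count as DLTs.* No other DLT criterion changes, and irinotecan reductions under Table 5 do not become DLTs.

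The 48-hour limit is a proposal by analogy with the Table 5 dosing row, not an existing definition; the sponsor may choose another. The antidiarrheal regimen should be named so that sites apply the rule alike. For nausea and vomiting, investigators already make the refractory distinction under Table 8, footnote a.

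The text change is one line and one sentence in two places, with no added visits or procedures. A changed DLT definition would probably be a substantial modification under section 13.6. The operating cost is some extra expansion or earlier stopping: under the independence assumptions, expansion from 3 to 6 patients rises from 24% to 28%-32% with 10% other DLTs, and from 38% to 40%-42% with 20%.
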